Immunoglobulins (IgG) have been placed on the ocular surface in the form of autologous/allogeneic serum/plasma eye drops for treating ocular surface diseases. Blood derived products (unfractionated serum or plasma eye drops) are essentially physiological IgG formulations, therefore clinical data pertaining to their use in treating ocular surface diseases is relevant to the proposed fractionated plasma product (IVIG eye drops). This is because the IgG concentration in unfractionated serum/plasma eye drops (50%) and the proposed IVIG eye drops is similar (4 mg/ml). Normal average serum IgG values are 10 mg/ml.^{11, 29} Serum also contains important nutritive elements (such as vitamin A, epidermal growth factor, transforming growth factor- β , fibronectin, nerve growth factor and insulin-like growth factor) that promote the viability of ocular surface cells.³⁰⁻³⁴ Serum can be formulated as autologous or allogeneic serum tear eye drops in specialized laboratories or compounding pharmacies. Autologous serum drops are produced from the patient's own peripheral blood, whereas Allogeneic serum drops made from voluntary donors.^{35, 36}

Autologous Serum eye drops have been used for the treatment of ocular surface disorders, including dry eye, neurotrophic keratitis, exposure keratitis, graft-versus-host disease, Sjögren syndrome, and mucous membrane pemphigoid.³⁷⁻⁴⁹ Controlled clinical trials have shown the superiority of autologous serum eye drops compared with artificial tears when used to treat some of these conditions.^{43, 50, 51} Our research findings lead us to posit that IgG in serum contributes to its beneficial effects in autoimmune and inflammatory ocular surface diseases.

Although autologous serum is more commonly used, **Allogeneic serum eye drops** made from voluntary donors⁵² have been used in Denmark,⁵³ Norway,⁵⁴ and the Netherlands^{55, 56} as a means of minimizing the hazards and costs associated with the preparation of an autologous product. Allogeneic serum may be an appropriate alternative for selected patients who would benefit from serum treatment but whose autologous serum is unavailable or unsuitable.^{52, 57-60}

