1.12 Dose Rationale and Risk/Benefits

Proposed dose: IVIG eye drops 4 mg/ml (0.4%) two times a day.

Rationale: Serum eye drops, compounded by diluting serum by 50% in normal saline, are routinely used for treating ocular surface diseases. The amount of IgG in undiluted serum is approximately 10 mg/ml, therefore 50% serum eye drops has approximately 5 mg/ml IgG, and serum eye drops are generally used four times a day. Since, at 50% dilution serum eye drops are effective in treating ocular surface diseases, we have proposed a similar dose of IgG in IVIG eye drops (4 mg/ml). In our in vitro experiments, we have determined 4 mg/ml IVIG to be non-toxic, as this dose, when added to medium of cultured epithelial cells for 24 hours, did not cause an increase in LDH concentration in the supernatant.

Also, it is generally accepted that IVIG should be given at a concentration that is at least 4 times the concentration of IgG at the application site. In ocular surface diseases, we have estimated IgG amount on the ocular surface to be approximately 0.5 mg/ml, therefore the IVIG dose should be at least 2 mg/ml to be effective. Taken together, our proposed dose of IVIG eye drops replicates the clinically in-use dose of IgG in serum tears, is non-toxic in vitro, and above the threshold required to be effective.

Adverse Effects of IVIG Treatment: To date, IVIG has been administered via systemic route only. Mild to moderate adverse reactions to high-dose IVIG therapy might be seen in nearly 30% of patients. Some of the common adverse reactions include fever, headache, chills, nausea, hypotension, and muscle cramps. Temporary cessation of the IVIG infusion, slow infusion, and use of general anti-inflammatory agents can control these events. Switching to SCIG is another viable alternative. Anaphylaxis can occur in IgA-deficient patients and use of low IgA-containing IVIG preparations is recommended in such cases. Other effects include meningeal inflammation and aseptic meningitis due to the release of inflammatory cytokines and neutrophil activation by IgG Abs within IVIG that mimic antineutrophil cytoplasmic Abs; intravascular hemolysis due to the presence of anti-A or anti-B isoagglutinins or less commonly anti-D or anti-K Abs; thromboembolism because of contamination of IVIG with clotting factors and formation of platelet-leukocyte aggregates; and renal complications due to osmotic injury that could be prevented by using non-sugarstabilized IVIG.

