5.6 Prior and Concomitant Therapy

Prior medications are defined as all medications taken within 30 days prior to Day 1, whether there is continued use or not. Concomitant medications must be identified in the subject's medical record, including all lubricants administered for Dry Eye Disease. These medications will be recorded in the case report form (CRF).

- For each medication taken, the following information will be collected:
 - Medication trade name
 - Eye that was treated, if applicable
 - Indication for which the medication was given

- Date started
- Date stopped
- Dose of medication used.

In general, patients will be required to maintain the treatments that they were using at entry into the study throughout the follow-up period. Patients will be instructed to continue using the same brand of eye drops during the study as they were using at the screening visit. If patients are wearing contact lenses (Soft bandage contact lenses or PROSE lens) or using serum tears, they will be asked to discontinue contact lens wear or use of serum tears for 2-weeks prior to being enrolled (Baseline visit) and will be required to not wear contact lenses or use serum tears for the duration of the study (until week 10 visit). This is necessary as one of the proposed exploratory study outcome measure is corneal Staining. Contact lenses can directly reduce corneal epitheliopathy and staining due to ensconcing and acting like a bandage that prevents corneal exposure to tear fluid inflammatory materials. Thus, because of overlapping effects on the exploratory outcome measure, it may not be possible to attribute any observed clinical benefit to IVIG-eye drops treatment if contact lenses are used concurrently. This approach has been used in other clinical trials that have investigated the use of an anti-inflammatory agent in dry eye disease (NIH funded 'Dry Eye Evaluation and Management (DREAM) study').⁶⁴ Stopping contact lens wear may increase the risk of worsening of Dry Eye Disease (DED) during the wash-out period and during the course of the study. However, because other eye drop treatments will continue during the wash out period as well as during the course of the study, we do not expect any significant clinical worsening during the study. We do however expect the frequency of use of artificial tears to go up during the wash out period and during the course of the study.

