Patients will be enrolled if they have been using their eye treatments for at least 30 day prior to the baseline visit and patients will be asked to commit to continue using the same treatments for the duration of the study. Participants will also be permitted to continue ancillary treatments such as eyelid massage or warm compresses of the eyelids. The number of drops and frequency must be recorded in the subject diary provided. The use of any investigational agent during past 30 days is prohibited.

The subjects will be monitored at 4 week intervals to ensure that they are not subjected to any undue risks during the course of the study. Additionally, they will be warned of the possible signs and symptoms of clinical worsening of DED, and advised to contact the research team immediately in case any of those symptoms occur. Subjects will also be encouraged to contact the research team in case they experience any ocular discomfort during the wash out period or during the course of the study. The subject's condition will be monitored by the physician (Principal Investigator) at each study visit, as well as at any interim visit (in case of adverse symptoms, as mentioned above). Any worsening of DED or any adverse event due to the study drug will be recorded. In case of clinical worsening, based on the individual subject's clinical condition, one or more of the following therapeutic decisions may be implemented: (1) Increasing/adding the use of artificial tears or ointments (2) Increasing/adding the use of anti-inflammatory therapy (Restasis/ Xiidra/ Steroids) or Serum Tears, (3) Withdrawal of the use of study drug (if worsening occurs during the course of the study). The decision will be made by the physician (Principal Investigator) based upon his clinical judgment as per the individual subject's clinical condition. If contact lens wear is instituted during the course of the study and/or the study drug is withdrawn, the subject will be withdrawn from the study. After any clinical worsening is noted, the subjects will be followed more closely (weekly) until complete resolution of symptoms and return to the subject's previous baseline. Subjects will be withdrawn from the study for presumed ocular allergic reaction to the product and ocular infection. The study will be stopped if the incidences of presumed ocular allergic reaction to the product and ocular infection surpasses 20% for each.

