5.7 Rescue Plan

The research staff, including the PI, will be masked to randomization, thus will not be aware if a particular subject receives study drug or placebo. Subjects will be monitored by the Principal Investigator at each study visit. Any worsening of DED or any adverse event (AEs) will be recorded and in the case of AEs followed to resolution. In case of clinical worsening/ adverse event(s), based on the individual subject's clinical condition, one or more of the following therapeutic decisions may be implemented:

- (1) Increasing/adding the use of artificial tears or ointments,
- (2) Increasing/adding the use of anti-inflammatory therapy (Restasis/ Xiidra/ Steroids) or Serum Tears
- (3) Discontinue the study drug.
- (4) Other eye drops/measures (example, contact lens or surgeries), if indicated.

The decision will be made by the Principal Investigator based on his clinical judgment and the individual subject's clinical condition. If contact lens wear is reinstated and/or the study drug is discontinued, the subject will be withdrawn from the study. If an adverse event is severe enough to discontinue the subject from the study, the PI may decide to break the subject's randomization code if it seems relevant to the treatment of his/her ocular condition at that time. He/ She will receive the treatment required for his/ her eye condition as per established clinical guidelines.

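### Serum tears are barred to week 10 yet allowed as rescue with no stated consequence; for 7 of 15 exploratory endpoints, a subject on serum at week 8 has no serum-free on-treatment value

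*Combined protocol and SAP*

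**What the plan says.** Sections 4.2, 5.6 and 6.5.1 tell subjects on contact lenses or serum tears to stop two weeks before baseline. Section 5.6 adds that they "will be required to not wear contact lenses or use serum tears for the duration of the study (until week 10 visit".

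Sections 5.6 and 5.7 then list what the investigator may do if a subject worsens. One option is "Increasing/adding the use of anti-inflammatory therapy (Restasis/ Xiidra/ Steroids) or Serum Tears". Section 5.6 names the steps that end participation: "If contact lens wear is instituted during the course of the study and/or the study drug is withdrawn", the subject is withdrawn. Section 5.7 says the same: "If contact lens wear is reinstated and/or the study drug is discontinued, the subject will be withdrawn from the study". Starting serum tears appears in neither sentence.

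The protocol sees serum as close to the study drug. Section 1.11.2 justifies using clinical data on serum drops as follows: "This is because the IgG concentration in unfractionated serum/plasma eye drops (50%) and the proposed IVIG eye drops is similar (4 mg/ml". It also states: "Our research findings lead us to posit that IgG in serum contributes to its beneficial effects in autoimmune and inflammatory ocular surface diseases". Section 1.12 bases the study dose on serum drops.

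Sections 7.2 and 7.3 do not mention rescue. The intention-to-treat set keeps every randomised subject whatever the adherence or deviation. The per-protocol set keeps those who finished treatment as intended, with no list of disqualifying deviations.

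**The concern.** A saline subject who worsens, starts serum tears and keeps using the study drops is receiving topical IgG at week 8 while being summarised as a control. Nothing in the plan removes that subject from the per-protocol set, because the study treatment was completed. An IVIG subject on serum receives extra IgG and serum's other constituents.

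No efficacy test is planned, but the numbers will be used. Section 7.2 reports a treatment effect size, section 7.1 wants SD estimates for the next sample size, and section 1.5 says the results will decide the primary endpoint or endpoints of later studies. Serum use among saline subjects can narrow the contrast and serum use among IVIG subjects can widen it. Rescued subjects also start from a worse state. The net direction is unknown.

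The visit schedule makes later repair difficult. Concomitant-medication records (section 5.6) give start and stop dates, so serum users can be identified, but a pre-serum value that was never measured cannot be recovered.

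**Working it through.** **Arm sizes.** Section 7.1 wants 12 per arm and allows 10% attrition: 12 / (1 − 0.10) = 13.3, rounded up to 14 per arm, or 28 in total. This reproduces the recruitment target and the 14 per group in section 3.1.

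**Which endpoints have only week 8 after baseline.** The 15 numbered endpoints of section 3.4 set against the schedule of visits and sections 3.6 and 6.5.3 to 6.5.5:

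| Endpoint (number in 3.4) | Measured after baseline |
|---|---|
| Schirmer I (2) | week 8 |
| Corneal staining clearance (3) | week 8 |
| Corneal staining score (4) | week 8 |
| NIK BUT (12) | week 8 |
| Keratograph redness (13) | week 8 |
| MMP-9 (14) | week 8 |
| Cytokines in surface wash (15) | week 8 |
| OSDI, VBR redness, visual acuity, drop frequency, filaments, mucoid films, CGI, SGA (1, 5 to 11) | weeks 4, 8 and 10 |

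Count: 7 of 15. Symptom intensity (section 3.4.8) is described as an exploratory endpoint but is not in the numbered list; it is taken at weeks 4, 8 and 10, and counting it gives 7 of 16.

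The early-withdrawal visit in section 4.4.2 follows the week-10 list plus the tolerance scale, so it contains none of the seven. After worsening, section 5.6 says "the subjects will be followed more closely (weekly) until complete resolution of symptoms", but names no tests for those visits.

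**Nominal IgG exposure.** Relative daily IgG per eye = concentration × drops per day, assuming equal drop volume.

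- Study drug: 4 mg/ml × 2 = 8.
- Serum at the protocol's usual use. Section 1.12 says: "therefore 50% serum eye drops has approximately 5 mg/ml IgG, and serum eye drops are generally used four times a day". At 5 mg/ml, 5 × 4 = 20 and 20 / 8 = 2.5. At the 4 mg/ml of section 1.11.2, 4 × 4 = 16 and 16 / 8 = 2.0.
- The rescue text fixes neither strength nor frequency. Assumed alternatives: 50% twice daily, 8 / 8 = 1.0 to 10 / 8 = 1.25; 20% four times daily (2 mg/ml from 10 mg/ml undiluted), 8 / 8 = 1.0; 50% six times daily, 24 / 8 = 3.0 to 30 / 8 = 3.75.

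These are ratios of nominal dose, not of effect.

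**Weight of one subject.** 1 / 14 = 7.1% of an arm mean, or 7.1 percentage points of the staining-clearance proportion; 1 / 12 = 8.3%.

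**Chance that it happens at all.** The documents give no rescue rate. If each saline subject had an assumed probability r of starting serum, P(at least one) = 1 − (1 − r)^n. For n = 12: 46%, 72% and 93% at r = 5%, 10% and 20%. For n = 14: 51%, 77% and 96%. These show only how the chance depends on the assumed rate.

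**The case against.** **The analysis sets already settle it.** A reader might infer that no rule at all covers data after rescue. The documents do not support that. The intention-to-treat wording keeps subjects despite deviations and whatever they received, and its natural reading is that values are used as observed. What remains open is the per-protocol set. One can argue that a subject using a barred drop has not had the treatment as planned, but a subject who finished all study drops also fits the wording literally.

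**Allowing a restricted drug as rescue is ordinary.** True. The ban is also addressed to existing lens and serum users, and the reason section 5.6 gives concerns the bandage effect of lenses, not IgG. Rescue should stay available. The point is only that serum, unlike lenses, has no stated consequence although the protocol itself treats it as close to the study drug.

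**Any rescued saline subject lacks a clean value.** A reader might infer this too. It is too strong: it holds only for rescue with serum, still in use at week 8, and only for the seven endpoints.

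**Serum is not the only problem drop.** This stands. Section 4.2 permits steroids, Restasis and Xiidra at unchanged frequency, so adding or increasing them is also a departure. They add no IgG, but the plan should say how they are handled.

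**The consequence is small.** Largely right. There is no primary efficacy endpoint and no efficacy test, section 5.6 expects no significant worsening, and endpoint 7 may capture added drops. That limits the importance of the point, but does not supply the missing measurements.

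**Conclusion.** The gap is real and modest. A saline subject given serum tears can finish the drops and count in both effect-size summaries, the per-protocol one on a literal reading. If serum is still in use at week 8, 7 of the 15 listed endpoints have no serum-free on-treatment value for that subject. Each such subject weighs 7.1% of a 14-subject arm, or 8.3% of 12. At the protocol's own figures for usual serum use, nominal daily IgG would be 2.0 to 2.5 times that of the IVIG arm, assuming equal drop volume.

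The effect is confined to exploratory effect-size and SD estimates. The primary tolerability endpoint and the safety analysis are unaffected. A reader might infer that the effect size will be pulled towards no difference; the documents do not support a direction or a size, because they give no rescue rate and serum may be used in either arm.

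**What to change.** 1. **Sections 5.6, 5.7 and 4.4.2.** If serum tears are to be started before the week-8 assessments, then where clinically safe do the section 4.4.2 procedures plus Schirmer I and lissamine staining before the first serum drop. Continue follow-up to week 10, with no mandatory withdrawal.
2. **Section 7.3.** Exclude from the per-protocol set subjects who start serum tears before the week-8 assessments. State whether newly added or increased steroids, Restasis or Xiidra are treated the same way.
3. **Section 7.2.** Keep the intention-to-treat summary on all observed values as the lead. Add a supplementary summary using pre-serum on-treatment values where they were measured, and report their timing. For endpoints with no such value (12 to 15, and 2 to 4 if the added tests were not done), treat the subject as missing in that summary. Do not carry baseline forward, which would set the change to zero by construction. Report the numbers starting serum tears and other rescue by arm.

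The cost is two tests already in the protocol, done at an interim visit, plus a few sentences and a slightly smaller per-protocol set. The pre-serum values will come earlier than week 8 and at a time of worsening, which is why they belong in a supplementary summary.

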3.5 Safety Endpoints

Safety assessments include Vital Signs, recording of all complications and adverse events, as well as ophthalmic exam findings. All ocular and non-ocular adverse events will be assessed for severity and relationship to the investigational product.

In addition to the primary tolerability endpoint (Section 2.2), the following safety endpoints will be assessed:

- The proportion of screened subjects who are successfully recruited in the study (i.e., recruitment rate)
- The proportion of eligible subjects at Day 56 who successfully complete (i.e., retention rate, (non)compliance or adherence rate) a full eight weeks (i.e., 56 days) of therapy with topical administration two times per day (BID).
- All reported adverse events, classified by frequency, severity, and relatedness, from baseline (Day 1) through the last study visit (Day 70).
- Clinically significant changes in vital signs or ophthalmic examination from baseline.

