4.4.2 Data Collection and Follow-up for Withdrawn Subjects

If a subject withdraws from the study prior to 8 weeks, the subject will be asked to complete the procedures outlined in the 10 week visit as well as the Test Substance Tolerance scale from 8 weeks, as soon as possible. Subjects who voluntarily withdraw from the study between 8 weeks and 10 weeks will be asked to complete procedures outlined in the 10 weeks visit as soon as possible. Subjects who are withdrawn due to adverse events will be followed at least until resolution or stabilization of the adverse event.

If the subject remains in the study for safety evaluation, follow-up visits will be scheduled according to the schedule of visits and procedures found in the synopsis.

5 Study Drug

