All AEs and SAEs whether volunteered by the subject, discovered by study personnel during questioning, or detected through physical examination, laboratory test, or other means will be reported appropriately. For each adverse event, the following information will be recorded on the subject's Case Report Form(s): onset date, end date or continues, intensity, duration, relationship to test patch, action taken, and outcome. If a subject experiences a serious adverse event (SAE), study staff may discontinue the subject from study participation. The study staff must notify the IRB within 24 hours of receipt of the information. The study staff will instruct the subject to notify the research facility should any adverse event occur within 7 days of study completion. (For definitions of an AE and SAE, see below). Subjects who withdraw due to an adverse event may be replaced.

- **Serious Adverse Event:** An AE should be classified as an SAE if the following criteria are met:
 1. It results in death (i.e., the AE actually causes or leads to death.).
 2. It is life-threatening (i.e., the AE, in the view of the investigator, places the subject at immediate risk of death. It does not include an AE that, had it occurred in a more severe form, might have caused death.).
 3. It requires or prolongs inpatient hospitalization.
 4. It results in persistent or significant disability/incapacity (i.e., the AE results in substantial disruption of the subject's ability to conduct normal life functions).

5. It results in a congenital anomaly/ birth defect in a neonate/infant born to a mother exposed to the investigational medicinal product (IMP).
6. It is considered a significant medical event by the investigator based on medical judgement (e.g., my jeopardize the subject or may requires medical or surgical intervention to prevent any of the occurrences listed above.

To ensure consistency of AE and SAE causality assessments, the following general guideline will be applied:

Yes

There is a plausible temporal relationship between the onset of the AE and administration of the IVIG, and the AE cannot be readily explained by the subject's clinical state, intercurrent illness, or concomitant therapies; and/or the AE follows a known pattern of response to the IVIG; and/or the AE abates or resolves upon discontinuation of the IVIG or dose reduction and, if applicable, reappears upon re-challenge

No

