Evidence exists that the AE has an etiology other than the IVIG (e.g., preexisting medical condition, underlying disease, intercurrent illness, or concomitant medication); and/or the AE has no plausible temporal relationship to IVIG administration (e.g., cancer diagnosed 2 days after first dose of study drug)

Life-threatening: Any adverse drug experience in which the subject was at risk of death at the time of the event. It does not refer to an event which hypothetically might have caused death if it were more severe.

Expected adverse event: Expected adverse events are those adverse events that are listed or characterized in the Package Insert (P.I) or current Investigator Brochure (I.B).

Unexpected adverse event: Any adverse event, the specificity or severity of which is not consistent with the current Investigator's Brochure.

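### Relatedness is worded against IVIG alone and may be rated after the investigator opens the code, so for code-broken adverse events it can depend on arm

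*Combined protocol and SAP*

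**What the plan says.** - **Masking and code break (5.7 Rescue Plan).** The plan states that "The research staff, including the PI, will be masked to randomization". If an adverse event is severe enough to take the subject out of the study, "the PI may decide to break the subject's randomization code if it seems relevant to the treatment".
- **Relatedness (8.1 Adverse Event Definitions).** *Yes* applies when "There is a plausible temporal relationship between the onset of the AE and administration of the IVIG" and no other ready explanation exists; and/or "the AE follows a known pattern of response to the IVIG; and/or the AE abates or resolves upon discontinuation of the IVIG". *No* applies when "Evidence exists that the AE has an etiology other than the IVIG" and/or "the AE has no plausible temporal relationship to IVIG administration". The section calls this a general guideline.
- **Other references for relatedness.** Sections 3.5, 8.6 and 8.8 relate events to the investigational product. The list of CRF items in 8.1 relates them to a test patch, which is not a product in this trial.
- **Use of relatedness (3.5 Safety Endpoints).** Adverse events are to be classified by frequency, severity and relatedness from Day 1 to Day 70.
- **Ratings at exit (4.4.2).** A subject who leaves before week 8 "will be asked to complete the procedures outlined in the 10 week visit as well as the Test Substance Tolerance scale from 8 weeks". No fixed date is set; this is to happen promptly after withdrawal. The week 10 procedures in 6.5.5 include the physician's global rating, the slit-lamp examination and the VBR redness score.
- **Who rates.** The PI gives the CGI (3.4.3), and the investigator performs the slit-lamp examination and VBR grading (3.5.2). The PI and his team are responsible for identifying adverse events (8.9). The documents do not name the causality rater outright, and no separate masked assessor is named.

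**The concern.** Safety and tolerability are the primary objective (section 2), and relatedness is one of the ways safety will be described. While the mask holds, the IVIG wording in 8.1 does little harm: a rater who does not know the arm has to judge every event as if the drop might be IVIG, so both arms are treated alike. The difficulty arises when that wording meets an opened code. A known saline subject and a known IVIG subject with the same event at the same time are then judged by a rule that gives them different answers. This can happen only for events that end participation, and no text prevents it.

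The PI's other exit ratings (CGI, slit lamp, VBR) are also unprotected. For these the risk is influence on a rater who knows the arm. The rule itself does not force a different answer.

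**Working it through.** There is no stated figure on this point to reproduce. The check is mainly a reading of the sections against one another, followed by simple arithmetic for scale.

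**Step 1: apply 8.1 to one event under three states of knowledge.**

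| Limb in 8.1 | Arm unknown | Known saline | Known IVIG |
|---|---|---|---|
| *Yes*: timing relative to IVIG | can be met | cannot be met; none was given | can be met |
| *Yes*: known pattern of response to IVIG | can be met | no response to IVIG is possible | can be met |
| *Yes*: abates when IVIG is stopped | can be met | cannot be met; none was stopped | can be met |
| *No*: no plausible timing relative to IVIG | depends on the event | always met | depends on the event |

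The pattern limb could be stretched to mean mere resemblance, but the last *No* limb would still be met for a known saline subject.

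**Step 2: can rating follow the code break?** The third *Yes* limb can be judged only once the drop has been stopped, and 5.7 permits the code to be opened from that same point. Section 8.5 continues evaluation until the event resolves or the subject is stable, and 4.4.2 collects the exit ratings after withdrawal. The sequence of break first and rating second is therefore open, although nothing prescribes it.

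**Step 3: denominators.** Section 7.1 plans 12 per arm and allows 10% attrition: 12/(1 − 0.10) = 13.3, rounded up to 14 per arm, or 28 in all, matching 3.1 and 7.1. Equal arms are assumed below.

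**Step 4: one reclassified event**, counting subjects with at least one related event and taking this to be the subject's only one:

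- 14 per arm: 1/14 = 7.1 points.
- 12 per arm: 1/12 = 8.3 points.

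For proportion, exact (Clopper-Pearson) 95% intervals at 14 per arm are 0 to 23.2% for 0/14 and 0.2 to 33.9% for 1/14.

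**Step 5: an illustration on assumed inputs.** Suppose each arm has one identical code-broken event, and a masked rater would say *Yes* with chance m in either arm (assumed 0.25 to 1).

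- Rated masked: m/14 − m/14 = 0.
- Rated after the break: saline contributes 0 and IVIG between m and 1. The artificial difference is from 0.25/14 = 1.8 points to 1/14 = 7.1 points. At 12 per arm it is 0.25/12 = 2.1 to 1/12 = 8.3 points.

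Neither m nor the number of code breaks comes from the documents.

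**The case against.** The strongest reply is that the order of events is inferred. Section 5.7 says that adverse events will be recorded before it mentions the code, and no section puts the break ahead of the rating. That is right: this is a gap and not an instruction. It still stands as a gap, because one *Yes* limb needs information available only at or after discontinuation.

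A second reply is that 8.1 is only a guideline and that 3.5, 8.6 and 8.8 refer to the investigational product. That weakens any claim that the plan rigidly imposes an IVIG-only rule. It also shows three different references for one endpoint, one of them to a product not in the trial, and these have to be reconciled in any case.

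Third, the route is narrow. It needs an event that ends participation and a judgement that the code matters for treatment. Opening the code for care is legitimate and is not the fault here.

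A reader might also infer that severity, CGI and the tolerance VAS differ between arms by construction. The documents do not support this:

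- Severity is defined in 8.2 without reference to treatment, and 5.7 requires the event to be judged severe enough for discontinuation before the code is opened.
- The CGI is at most open to influence.
- The subject marks the VAS (3.2), so it is exposed only if the subject learns the arm, which no section says will happen. Nor does any section say that the exit VAS replaces the week 8 value in the primary tolerability endpoint.

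**Conclusion.** The point holds in limited form and is minor. For a code-broken event rated after the break, the 8.1 wording can make relatedness depend on the arm, and nothing in the plan prevents or flags this. The size is 7.1 points (14 per arm) or 8.3 points (12 per arm) for each reclassified event in an arm, given equal arms and one such event per subject.

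Two limits apply. The adverse event and SAE rates with 95% intervals in 7.2 are unaffected, because 8.1 counts events regardless of attribution; only the relatedness breakdown moves. And the total effect cannot be stated. A reader might take the 10% attrition allowance (0.10 × 28 = 2.8, about 3 subjects) and infer a shift of 3/14 = 21.4 points. That would require every expected dropout to be an adverse event discontinuation, code-broken, rated afterwards and reclassified. The 10% in 7.1 is general attrition, and the documents give no number of code breaks.

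**What to change.** 1. **One reference for relatedness.** Use study medication (IVIG or saline) in 3.5, in both the *Yes* and *No* definitions of 8.1, in the 8.1 CRF item that now names a test patch, and in 8.6 and 8.8.
2. **Order of recording.** In 5.7 and 4.4.2, state that, except where immediate care requires the code first, relatedness, the PI's exit ratings (CGI, slit lamp, VBR) and the subject's tolerance VAS are recorded and dated before the code is opened.
3. **Traceability.** Log every code break with date and time. Flag any rating made after it and report such ratings separately.

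Leave the clinical grounds for opening the code as they are. With these changes, the same event rated under the mask has the same chance of *Yes* in both arms. The cost is wording in six sections (3.5, 4.4.2, 5.7, 8.1, 8.6, 8.8), a simple log, one CRF date/time field and a short delay to a non-urgent code break. No visit, test or staff is added. The changes should be in place before the first code break, since a masked rating that was not recorded cannot be recovered.
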